6.2 AUXILIARY TREATMENTS

Not applicable, no auxiliary treatments will be administered during this study.

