This study will involve the subjects' exposure to ionising radiation, due to the administration of a radiotracer and the performance of a transmission scan (see Section 7.2.1). Long-term exposure (years or decades) to ionising radiation can cause cancer. The risk of developing cancer as a consequence of taking part in this study is less than 0.01%, which is considered as negligible risk (for comparison, in the general population, the natural lifetime cancer incidence is around 50%) [19], [20]. The radiation dosimetry for this study is summarised in Table 1 below. The radiotracer technetium-99m (99mTc) albumin colloid will be used in this study. Each subject will receive a maximum of 4 administrations of 99mTc-albumin throughout the course of the study, with a target dose of 1-2 MBq per administration (see Table 1). Transmission scan will be performed once during the study, using a planar 57-Cobalt (Co-57) sheet source which has a total effective dose of 0.07 mSv

Clinical Study Code No.: CLI-05993AB6-06	Version No.: 1.0	Date: 16 February 2023
EudraCT number: 2022-003247-97		

per scan. The radiation dose to be administered in this study has been reviewed by the appointed Medical Physics Expert and Clinical Radiation Expert, in line with current regulations. As a precautionary measure, subjects with a historical exposure (5 mSv in the last 12 months or 10 mSv in the last 5 years) or a total dosimetry value which contraindicates their participation will not be allowed in this study (see [Section 4.3](#), exclusion criteria #18 and #19). Each subject will receive a maximum total ionising radiation exposure of 0.27 mSv. This is equivalent to approximately 1 month of average natural background radiation dose in the United Kingdom (UK) or around 14 chest posteroanterior x-ray examinations.

Table 1. Radiation dosimetry of the study

Procedure	Radioactivity per administration	Number of administration	A Total Dose (MBq)	B Effective Dose per administration (mSv)	Total Effective Dose (A x B)
Co-57 transmission scan	-	1	-	-	0.07 mSv
Inhalation of 99mTc- albumin colloid	1-2 MBq	4	8 MBq (maximum 2 MBq per administration)	0.05 mSv	0.2 mSv

99mTC= Technetium-99m; Co-57=57-Cobalt.

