10. Documented history of drug abuse within 12 months prior to screening or a positive urine drug screen evaluated at screening or prior to randomisation;
Note: In case of a positive test, the test can be repeated once before randomisation.
11. Intake of non-permitted concomitant medications in the predefined period prior to screening or prior to randomisation, or subject expected to take non-permitted concomitant medications during the study;
12. Presence of any current infection, or previous infection that resolved less than 1 week prior to screening or to randomisation;
13. Known intolerance and/or hypersensitivity to any of the excipients contained in the formulation used in the study;
14. Documented coronavirus disease 2019 (COVID-19) diagnosis within the last 2 weeks, or associated complications/symptoms which have not resolved within 2 weeks prior to screening or prior to randomisation;
15. Heavy caffeine drinker (average of > 5 cups or glasses of caffeinated beverages [e.g. coffee, tea, cola], calculated by the number of standard espresso portions, per day);
16. For females only: pregnant or lactating women, where pregnancy is defined as the state of a female after conception and until termination of the gestation, confirmed by a positive serum human chorionic gonadotropin laboratory test;
Note: A serum pregnancy test will be performed at screening only. A urine pregnancy test will be collected on Day -1 of each treatment period.
17. The use of any kind of smoking electronic devices (e.g. e-cigarettes), within 6 months before screening or prior to randomisation;
18. Subjects for whom participation in this study will exceed a total radiation exposure of 5 mSv in the last 12-month period or 10 mSv in the last 5-year period;
19. Subjects with a total dosimetry value (including history of exposure through occupation) which, according to the Investigator's or a medically qualified designee's judgement, contraindicates their participation in the study.

The following criteria will be re-checked before randomisation: #7, #8, #9, #10, #11, #12, #14, #16 and #17.

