7.2 STUDY ASSESSMENTS AND PROCEDURES

7.2.1 MUCOCILIARY CLEARANCE ASSESSMENT

Image acquisitions for MCC assessments, the transmission scan and the background scan will be performed at the timepoints specified in [Table 2](#).

On Day -1 of TP1 (before the assessment of MCC), the gamma scintigraphy procedure will be performed and will consist of a single transmission scan of the thorax, performed using a planar Co-57 source. The procedure will provide an outline of the lungs for use in subsequent analysis. A single background scan will also be performed during this visit, to account for background radiation. Subjects will be standing in front of the camera and any radioactive substance (except the markers) will be removed from the room.

On each visit with MCC assessments (see [Table 2](#)), subjects will be administered 99mTc-albumin colloid via a standardised aerosol delivery procedure. Controlled breathing conditions will be implemented using a metronome and commercial visual flow signal. A Mini 900 Ratemeter will be used to target a dose of 1-2 MBq (maximal dose of 2 MBq per administration). To assure that this adequate dose is achieved, the probe will be shielded with approximately 1 mm lead and will be taken from the middle of a subject's back. Inhalation time will vary by subject size and deposition efficiency, but is expected to be around 2 minutes per subject.

Gamma scintigraphy imaging will be performed over 240 minutes. Image acquisition will begin after completing the 99mTc-albumin administration, and the analysis of these images will provide a measurement of MCC. Anterior and posterior images of a 2-minute duration will be taken at 0 (immediately), 15 minutes, 30 minutes, 1 hour, 1 hour 30 minutes, 2 hours, 2 hours 30 minutes, 3 hours and 4 hours after the administration of the radiotracer. In order to allow accurate alignment of sequential images, an external anatomical marker containing a maximum of 0.02 MBq 99mTc will be taped to the subjects' chest and back, for the duration of the imaging procedures.

On Day 8 of each treatment period, the radiotracer will be administered post-dose, approximately 2 hours after administration of the last dose of the propellant.

Images will be reviewed and counts in each region of interest will be captured and corrected for background and radiation decay. To assess central *versus* peripheral deposition, the lung will be divided into central and peripheral (the area outside central) regions.

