8. STUDY ASSESSMENTS

The **primary objective** of this study is to assess the effect of multiple doses of the HFA-152a propellant and the HFA-134a propellant (when administered not in combination with active compounds) on MCC.

The MCC assessment will be performed on Day -1 and on Day 8 of each treatment period, as described in [Section 7.2.1](#).

The following **study variables** will be considered to **assess the primary objective** of the study:

- MCC rate, as assessed by the percent particle retention at 2 hours after the inhalation of radiolabelled particles (PPR₂);
- MCC rate, as assessed by the percent particle retention at 4 hours after the inhalation of radiolabelled particles (PPR₄).

Note: PPR in whole lung will be used for the assessment of the variables above.

The following **study variable** will **complete the evaluation of the primary objective** of the study:

- MCC, as assessed by the area under the tracheobronchial particle retention curve between 0 and 4 hours (AUC₀₋₄) after the inhalation of radiolabelled particles.

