10. ADVERSE EVENT REPORTING

10.1 DEFINITIONS

An **Adverse Event (AE)** is any untoward medical occurrence in a subject to whom a medicinal product is administered and which does not necessarily have a causal relationship with this treatment.

An AE can therefore be any unfavourable and unintended sign (including an abnormal laboratory finding), symptom, or disease temporally associated with the use of a medicinal product, whether or not considered related to the medicinal product.

An **Adverse Drug Reaction (ADR)** is a noxious and unintended response to an IMP related to any dose administered.

Clinical Study Code No.: CLI-05993AB6-06

Version No.: 1.0

Date: 16 February 2023

EudraCT number: 2022-003247-97

Within this study, the causality of an AE has to be considered with regards to the placebo and its excipients.

All AEs judged by either the reporting Investigator or the Sponsor as having a reasonable causal relationship to a medicinal product qualify as adverse reactions.

Adverse reactions could derive from medication errors and uses outside what is foreseen in the protocol in relation to the IMP, including misuse and abuse of the product.

A **Serious Adverse Event (SAE)/Serious ADR** is any untoward medical occurrence or noxious and unintended response to an IMP that, at any dose, falls into one or more of the following categories:

- **Results in death**

Death is not an AE but an outcome. It is the cause of death that should be regarded as the AE. The only exception to this rule is “sudden death” where no cause has been established; in this instance, “sudden death” should be regarded as the AE and “fatal” as its reason for being serious.

- **Is life-threatening**

“Life-threatening” refers to an event in which the subject was at risk of death at the time of the event (e.g. aplastic anaemia, acute renal failure, anaphylaxis). The term does not refer to an event which hypothetically might have caused death if it were more severe.

- **Requires hospitalisation or prolongation of existing hospitalisation**

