## 5.2 PHASES, PERIODS AND TIME POINTS

### 5.2.1 *Phases and periods*

Adverse events, medications, and procedures will be allocated to phases and periods. All other analyses will not be allocated to phases and periods. Instead, the visit and time point labels indicated on the subject's electronic case report form (eCRF) will be used to allocate the assessments to the correct treatment. Early termination and follow-up visit assessment will be allocated to the last administered treatment.

Adverse events and medications:

Phase	Period	Start	End
Screening		Date of signing the informed consent form (ICF), with 00:00 added as time part	First administration date(time) in the first available period – 1 minute
Treatment	Period 1	First administration date(time) in period 1	First administration date(time) in the next available period – 1 minute
	Period 2	First administration date(time) in period 2	Date of last contact, with 23:59 added as time part

Per definition, and for each subject, the first phase starts on the date of the earliest available ICF signature, with 00:00 added as time part. The last available phase/period ends on the date of last contact, with 23:59 added as time part.

Procedures:

Phase	Period	Start	End
Screening		Date of signing the informed consent form (ICF)	First administration date in the first available period – 1 day
Treatment	Period 1	First administration date in period 1	First administration date in the next available period – 1 day
	Period 2	First administration date in period 2	Date of last contact

Per definition, and for each subject, the first phase starts on the date of the earliest available ICF signature. The last available phase/period ends on the date of last contact.

All tables and figures will present treatments rather than periods.

	Statistical Analysis Plan	
CLI-05993AB6-06	Final Analysis	Final 1.0 of 05OCT2023

AEs, medications and procedures will be allocated to phases and periods as described in sections 3.1.2 and 4.5.2 respectively.

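### The inhaled radiotracer is covered by neither the hypersensitivity exclusion nor the AE causality item, and events starting after three of its four doses are tabulated under a propellant

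*Protocol*

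**What the plan says.** On whether the tracer is given:

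- Protocol 6.2 (Auxiliary treatments): "Not applicable, no auxiliary treatments will be administered during this study". Section 6, which describes the products administered, does not mention the radiotracer.
- Protocol 7.2.1: at each visit with MCC assessments, "subjects will be administered 99mTc-albumin colloid via a standardised aerosol delivery procedure".
- Protocol 1.3.1: "Each subject will receive a maximum of 4 administrations of 99mTc-albumin throughout the course of the study".
- Protocol 8: "The MCC assessment will be performed on Day -1 and on Day 8 of each treatment period".

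On eligibility, exclusion #13 in Protocol 4.3 reads "Known intolerance and/or hypersensitivity to any of the excipients contained in the formulation used in the study". Section 6.1.1 lists excipients only for the two inhalers. Exclusions #18 and #19 deal with radiation exposure.

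On adverse events:

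- Protocol 10.1: "Within this study, the causality of an AE has to be considered with regards to the placebo and its excipients". Section 10.4 then asks one yes/no question, on relatedness to study drug. The factors to be weighed include other treatments and protocol-related processes.
- SAP 3.1.1 lists treatment relationship as the only relatedness item collected. SAP 3.1.2 defines an ADR as a TEAE that is related to study treatment or has a missing relationship.
- Protocol 12.3.5 and SAP 3.1.3: events before the first study drug intake are pre-treatment and only listed. Later events are TEAEs, tabulated by treatment.
- SAP 5.2.1 ends Period 1 for adverse events at "First administration date(time) in the next available period – 1 minute", so Period 1 contains the wash-out and Day -1 of Period 2.

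**The concern.** Besides the two propellants, subjects inhale a third product, and the rules on eligibility and safety analysis do not deal with it.

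First, a volunteer with a known hypersensitivity to albumin or another tracer component meets no exclusion that names that hypersensitivity.

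Second, on Day 8 the tracer is inhaled about 2 hours after the propellant. Two inhaled agents given close together then share one causality question, which is framed around only one of them. If the investigator answers yes, the event becomes an ADR of a propellant. If it is also serious, Protocol 10.2 makes it unexpected by rule. If the answer is no, the event still sits in that propellant's TEAE count, and no item records that the tracer was suspected.

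Third, an event that follows the V5 tracer dose is charged to a propellant the subject stopped taking one to two weeks before.

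What is at stake is the secondary objective, the general safety and tolerability of each propellant. It is answered by descriptive counts in columns of about 20 subjects, where one subject is 1/20 = 5 percentage points.

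**Working it through.** **Reproducing the plan's own figures.** Two MCC days (Day -1, Day 8) × 2 periods = 4 administrations, which matches the stated maximum. Activity: 4 × 2 MBq = 8 MBq. Tracer dose: 4 × 0.05 mSv = 0.20 mSv. Adding the transmission scan: 0.20 + 0.07 = 0.27 mSv. All agree with Protocol 1.3.1. (The A × B heading in Table 1 would give 8 × 0.05 = 0.4. The stated 0.2 mSv is the number of administrations times the dose per administration. This does not affect the present point.)

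**Allocating an event to each tracer dose.** The rules are those of Protocol 12.3.5 and SAP 3.1.2, 3.1.3 and 5.2.1. The assumption is that the event starts soon after the tracer and before the next propellant dose.

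| Tracer dose | Classification | Column |
|---|---|---|
| V2 (Period 1, Day -1) | Pre-treatment AE, listed only | None |
| V4 (Period 1, Day 8) | TEAE | Period 1 propellant |
| V5 (Period 2, Day -1) | TEAE | Period 1 propellant, after 7 to 14 days of wash-out |
| V7 (Period 2, Day 8) | TEAE | Period 2 propellant |

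So 3 of 4 doses (75%) fall in a window tabulated under a propellant.

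**Totals.**

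- 20 completers: 20 × 4 = 80 administrations. Of these, 20 × 3 = 60 are in a propellant window (40 on Day 8, 20 at V5) and 20 are pre-treatment.
- 18 completers: 18 × 4 = 72. Of these, 18 × 3 = 54 are in a propellant window and 18 are pre-treatment.

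**Split between propellants.** Each completer has one Day 8 tracer dose under each propellant. The V5 dose goes to whichever propellant came first.

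- 20 completers, 10 per sequence: 20 + 10 = 30 for HFA-152a and 20 + 10 = 30 for HFA-134a.
- 18 completers, 9 per sequence: 18 + 9 = 27 each.
- 18 completers split 10 and 8 (an assumed imbalance): 18 + 10 = 28 against 18 + 8 = 26.

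These are numbers of administrations, not of reactions. The documents give no reaction rate for the tracer, so an expected number of events cannot be derived.

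**The V5 charge.** Protocol 1.1 reports a mean residence time of about 9 minutes for HFA-152a, against a wash-out of 7 to 14 days. The documents give no such figure for HFA-134a, which is the propellant charged in about half of the V5 cases.

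**Eligibility and causality.** These need no arithmetic. Of the criteria in Protocol 4.2 and 4.3, #13 is the only one on hypersensitivity, and its object is the excipients of the formulation. In Protocol 10.4 and SAP 3.1.1, the only recorded relatedness item concerns study drug.

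**The case against.** The tracer is a measuring agent, and its activity, dosimetry, delivery and timing are openly described. The protocol does not define an auxiliary treatment, so the sponsor may hold that a diagnostic agent is not one. That stands: the mismatch between 6.2 and 7.2.1 is a matter of classification to be reconciled, and correcting 6.2 alone would be clerical. A reader might infer that the other gaps flow from 6.2. They do not. Exclusion #13, Sections 10.1 and 10.4, and SAP 5.2.1 do not refer to it, and each would be unchanged if it were corrected.

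Other stronger readings also fail:

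- *That subjects have no safeguard against the tracer.* Exclusions #18 and #19, review by a Medical Physics Expert and a Clinical Radiation Expert, and ARSAC authorisation all apply. They cover radiation. What is missing is a hypersensitivity criterion.
- *That tracer reactions get no causality assessment.* The investigator must weigh protocol-related processes and other treatments. The answer can therefore be no, which keeps the event out of the ADR counts. Only the record of the suspected cause is lost.
- *That every tracer reaction lands under a propellant.* Events between the V2 tracer dose and the first propellant dose do not.
- *That all subjects receive four doses.* Four is a maximum, which completers reach.
- *That the Section 10.12 duty to report reactions to a marketed non-investigational product cannot work without a data item.* It binds the investigator directly.

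It is also fair to say that a TEAE is defined by time and not by cause, that all events are listed with onset day, and that the cross-over spreads tracer exposure almost evenly. The last point removes any claim of directional bias. The first two soften the problem without removing it: the summary tables still mix the sources, and a listing by onset day does not show what the investigator suspected.

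**Conclusion.** The point holds in a limited form, as an inexpensive improvement worth making. No criterion addresses known hypersensitivity to a product inhaled up to four times. No item records suspected relatedness to that product. Events after three of its four doses (up to 60 of 80 administrations with 20 completers, 54 of 72 with 18) enter a propellant's TEAE count, and those at V5 enter the count of the washed-out propellant.

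The effect is on each propellant's absolute TEAE counts. With balanced sequences these rise about equally, so the contrast between propellants is not pushed in a set direction. The MCC analyses are not affected.

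This rests on three assumptions: that events start soon after the tracer dose, that sequences stay roughly balanced among completers, and that the AE page collects what Protocol 10.4 and SAP 3.1.1 describe. The eCRF itself is not among the documents. How many reactions to expect cannot be said.

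**What to change.** 1. Reconcile Protocol 6.2 with 1.3.1 and 7.2.1, stating how the 99mTc-albumin colloid is classified.
2. Reconcile exclusion #13 with all the inhaled products given in the study, so that it also covers components of the radiotracer.
3. Add one yes/no item to the AE page: related to radiotracer or imaging procedure.
4. In the TEAE overview of SAP 3.1.3, add a separate row for TEAEs judged related to the tracer or procedure and not to study drug.

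If the eCRF can no longer be changed, flag in the AE listings the events with onset after tracer inhalation on Day -1 and Day 8. This shows timing but not suspected cause, so it is second best.

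Cost: protocol wording, one eCRF field and one table row. The wider #13 might exclude very few volunteers.

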6.3 PACKAGING

6.3.1 STUDY TREATMENT KIT

Treatment kits will be supplied to the Investigator as subject kits containing two treatment period boxes, each containing two pMDI devices (one with a canister identified with a green sticker, and one with a canister identified with a red sticker).

Treatment kits will be supplied in the following packages:

- **Immediate packaging:** two labelled canisters containing placebo HFA-152a propellant or placebo HFA-134a propellant for inhalation (one canister identified with a green sticker on the top, and one canister identified with a red sticker on the top), plus two labelled actuators;
- **Outer packaging (period box):** labelled box containing two canisters and two actuators to be used at one treatment period;
- **Outer packaging (subject box):** one labelled box containing two period boxes.

6.3.2 TRAINING KIT

Training kits will be supplied to the investigational sites. Each kit will consist of one box containing placebo HFA-134a propellant pMDI. The training kits will be used at screening only (see [Table 2](#)) and must be stored as specified in [Section 6.8](#).

Training kits will be supplied in the following packages:

- **Immediate packaging:** one labelled canister containing placebo HFA134a propellant pMDI, plus one labelled actuator;
- **Outer packaging (subject box):** labelled box containing one labelled canister and one labelled actuator.

6.3.3 RESCUE MEDICATION

Not applicable.

6.4 LABELLING

All labelling of immediate and outer packaging for training and treatment kits will be in English and will be compliant with Annex 13 of Volume 4 of the Good Manufacturing Practice [\[23\]](#) and according to the UK local law and regulatory requirements.

6.5 TREATMENT ALLOCATION

A balanced block randomisation list will be generated using a computerised system. Each subject will be assigned to one of the two possible sequences arranged in a 2x2 William design.

Each subject will be identified by a unique 4-digit code (SXXX) assigned at screening.

Clinical Study Code No.: CLI-05993AB6-06

Version No.: 1.0

Date: 16 February 2023

EudraCT number: 2022-003247-97

At randomisation (Day 1 of TP1), each eligible subject will be assigned the lowest randomisation number available (a unique 3-digits code [XXX]), according to a preestablished randomisation list:

- Subjects who do not meet the inclusion criteria and/or who meet the exclusion criteria at screening or prior to randomisation will not be eligible to enter the study. They will be considered as “screen failure subjects”;

Note: Screen failure subjects may be rescreened once. Rescreened subjects should be assigned a new participant number for the rescreening event.

- Subjects who fully meet the inclusion and exclusion criteria at screening or before randomisation will be eligible to enter the study;
- Subjects who prematurely terminate the study will be considered as “drop-out subjects”. These subjects cannot be screened again.

Note: If a subject is withdrawn or discontinued from the study after randomisation, the subject code and randomisation number will not be reassigned to another subject.

